## 5 Population

This is a single-center (Northwestern University) study. We intend to enroll 25 subjects of which 20 are expected to undergo the TAC-WD/EVL phase of the study.

We will select adult LT recipients without immune disease, active viral disease, and previous or combined organ transplantation to avoid the confounding of coexistent inflammatory/infectious processes and prior transplants on the biomarker analysis. We will also have two ‘checks’ for study continuation after initial enrollment. The first is at one to two months post-LT to ensure there is no contraindication to starting EVL, that renal/liver function is reasonably preserved and stable, and that there is a low predicted risk of future TAC WD. The second check is to determine if TAC-WD at 3 months ( $\pm$  1 month) is safe - similar criteria (no rejections, stable liver/renal function, etc) will be used.

### 5.1 Inclusion criteria

Patients must give written informed consent 90 days prior to transplant or up to 60 days after transplant) before any assessment is performed.

Patients eligible for inclusion in this study have to fulfill all of the following criteria:

#### **Inclusion/Exclusion criteria:**

##### *Inclusion Criteria:*

- Adult LT candidates  $\geq$  18 years of age

- Listed for or recent (within 2 months) recipient of deceased or living donor liver transplantation

## 5.2 Exclusion criteria

### Exclusion Criteria:

- Combined or previous organ transplantation
- HIV infection
- Inability to provide informed consent or comply with the protocol
- Transplantation for autoimmune liver disease (Autoimmune hepatitis, Primary Biliary Cirrhosis, Primary Sclerosing Cholangitis)

### Criteria for Study Continuation and EVL addition (1 to 2 months post-LT):

1. Currently on TAC + prednisone +/- MPA therapy with no contraindication to starting EVL (i.e. wound infection; significant proteinuria (urine prot/cr ratio  $\geq 1.0$ ), hepatic artery thrombosis/stenosis, cytopenias (WBC  $< 1.5$ , ANC  $< 1.0$ , Platelet  $< 30$ , Hemoglobin  $< 7$ ), other deemed by investigator)
2. No more than 2 rejection episodes or 1 steroid-resistant rejection requiring lymphodepletion therapy
3. No active biliary, infectious, or malignant process
4. eGFR  $\geq 30$  ml/min/1.73m^2
5. No significant liver function abnormalities (Direct bilirubin, AST/ALT, Alkphos  $\geq 2x$  elevated)
6. If on current or prior antiviral therapy, HBV and HCV viral load should be undetectable
7. No combined transplantation (e.g. should be primary liver transplant alone)

### Criteria for Study Continuation and TAC-WD initiation (3 months ( $\pm 1$ month) post-LT):

1. Tolerating TAC + EVL combination
2. Same other criteria as 1 to 2 months criteria above

For all time points above, a  $\pm 1$  month window is allowable except that EVL must not be started until  $\geq 1$  month post-LT and Visit 6 must occur  $\geq 2$  weeks after Visit 5

## **6 Treatment**

### **6.1 Investigational and reference therapy**

Zortress (Everolimus) is a macrolide immunosuppressant. Zortress® (Everolimus) is a macrolide immunosuppressant. The chemical name of everolimus is (1R, 9S, 12S, 15R, 16E, 18R, 19R, 21R, 23S, 24E, 26E, 28E, 30S, 32S, 35R)-1, 18-dihydroxy-12-[(1R)-2-[(1S,3R,4R)-4-(2hydroxyethoxy)-3-methoxycyclohexyl-1-methylethyl]-19,30-dimethoxy-15, 17, 21,23, 29, 35-hexamethyl-11, 36-dioxa-4-aza-tricyclo[30.3.1.0] hexatriaconta-16,24,26,28-tetraene-2, 3, 10,14,20-pentaone.

Everolimus inhibits antigenic and interleukin (IL-2 and IL-15) stimulated activation and proliferation of T and B lymphocytes. In cells, everolimus binds to a cytoplasmic protein, the FK506 Binding Protein-12 (FKBP-12), to form an immunosuppressive complex (everolimus: FKBP-12) that binds to and inhibits the mammalian Target Of Rapamycin (mTOR), a key regulatory kinase. In the presence of everolimus phosphorylation of p70 S6 ribosomal protein kinase (p70S6K), a substrate of mTOR, is inhibited. Consequently, phosphorylation of the ribosomal S6 protein and subsequent protein synthesis and cell proliferation are inhibited. The everolimus: FKBP-12 complex has no effect on calcineurin activity.

In rats and nonhuman primate models, everolimus effectively reduces kidney allograft rejection resulting in prolonged graft survival.

Everolimus pharmacokinetics has been characterized after oral administration of single and multiple doses to adult kidney transplant patients, hepatically-impaired patients, and healthy subjects.

### **6.2 Treatment arms**

All patients will be assigned to Zortress® (everolimus) at advised doses and trough levels. After enrollment criteria met, EVL will be added (goal trough level 5-8 ng/ml) and TAC reduced (goal trough level 3-5 ng/ml). When TAC is discontinued, EVL will be maintained at goal trough of 5-8 ng/ml and prednisone kept for at least the study time period (6 months ( $\pm 1$  month)) at 5 mg/day. See study design (Figure 6 in Appendices).

### **6.3 Treating the patient**

#### **6.3.1 Patient numbering**

Subjects entering the study will be given sequential numbers in the order they are screened, e.g.; 01, 02, 03....

### **6.3.2 Dispensing the study drug**

“Study drug” is obtained via a prescription from the physician and filled at any pharmacy (local walk-in/mail-order).

### **6.3.3 Study drug supply, storage and tracking**

Pharmacies should be storing the drug at room temperature: 25°C (77°F); excursions permitted to 15-30°C (59-86°F). Medication should be protected from light and moisture.

### **6.3.4 Instructions for prescribing and taking the study drug**

“Study” drug will be obtained via a prescription. Everolimus is taken orally twice daily with doses approximately 12 hours apart. Everolimus can be taken with/without food.

This is an approved drug for the following:

Kidney transplant in low-moderate immunologic risk. It is to be used in combination with basiliximab, cyclosporine (reduced dose) and corticosteroids.

It is also approved for use in liver transplantation. It is not to be administered earlier than 30 days post-transplant. It is to be used in combination with tacrolimus (reduced doses) and corticosteroids.

### **6.3.5 Permitted study drug dose adjustments and interruptions**

Per protocol to maintain the required trough levels of tacrolimus and everolimus therapy (Figure 6)

### **6.3.6 Other concomitant treatment**

Any medication (prescribed or over-the-counter), alternative/complimentary medication, any medical or surgical procedure that the subject takes or undergoes during the study must be reported to the study team and will be reported in the CRF. This is to ensure that any elevation in liver function tests or rejection episode is most likely related to immunosuppression withdrawal and does not have another cause outside of the study.

It is important to note that medications that are normally used in post-transplant patients (antivirals, antibacterials, and other prophylactic meds, along with other prescribed meds) are allowed in this protocol.

Medications with strong-moderate CYP3A4 inhibitors (cyclosporine, ketoconazole, erythromycin, verapamil) and CYP3A4 inducers (e.g., rifampin) may affect everolimus concentrations. In this case Zortress dose adjustments should be considered.

### 6.3.7 Study drug discontinuation and premature patient withdrawal

Subjects may be withdrawn from the trial at any time for any reason, either by choice or due to medical indications. Subjects who are non-compliant with study guidelines, medications and clinic examinations will be withdrawn from the study. The NU IRB may also discontinue the study at any point. The subjects will be fully informed of these actions. If patients are withdrawn prematurely, they will still be followed through the follow-up time period of the study as per standard medical care. These data are important to collect to determine differences in this group compared to those who completed the study.

### 6.3.8 Study completion and post-study treatment

Study will be completed at the six month ( $\pm$  1 month) time point post-liver transplantation

## 7 Visit schedule and assessments

**Table 7-1 Assessment schedule**

Visit**	1	2	3	4	5	6	7	At rejection***	Early Term./Study Comp.
Day	-90 to 0 +30 (Tx)	0	30	90	120	135	180		
Inc./Exc. Criteria	X		X	X	X				
Obtain informed consent	X								
Physical Exam			X	X	X		X		
Donor/Recipient Collections		X*							
Blood (Flow, PBMC, RNA, sera)			X*	X	X	X	X	X	
Tissue RNA								X	
Study Completion Form						X	X		X

\*unfunded and not mandatory for this protocol

\*\*  $\pm$  1 month window allowable

Visit 1 = Patient enrollment SOC visit (I/E criteria, informed consent)

Visit 2= Transplant SOC- if possible, donor spleen/lymph nodes and recipient lymph node/blood

Visit 3= Day 30 SOC visit- if Inc./Exc. criteria met, add everolimus and stop MPA if being used. Collect blood if possible (unfunded for this study).

Visit 4= Day 90 SOC visit- if Inc./Exc. criteria met, start tacrolimus withdrawal. Collect blood.

Visit 5= Day 120 SOC visit- if Inc./Exc. criteria met, stop tacrolimus. Collect blood.

Visit 6 = Day 135 visit- collect blood.

Visit 7= Day 180 SOC visit- Study termination. Collect blood.

\*\*\*At any biopsy concerning for rejection: Collect blood and tissue in RNAlater. If rejection, study termination.

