Peripheral blood bioassays will be performed pre-TAC-WD (1 to 2 months and 3 months ( $\pm$  1 month)), immediately pre-TAC-WD (4 months ( $\pm$  1 month)), 2 weeks post-TAC-WD (4.5 months ( $\pm$  1 month) post-LT), at biopsy-proven rejection in any phase of the study (before or after TAC-WD phase), and at 6 months ( $\pm$  1 month) post-LT (Timeline Figure 6). We will also store extra blood samples (funds not requested – See Exploratory Objectives). Liver biopsies for standard histology will be performed only for cause at the time of rejection and not required by the protocol – extra tissue placed in RNAlater will be collected (funds not requested). The blood biomarkers will be compared between the groups (AR vs. no AR). Additionally, the patients will be monitored as standard of care with clinical laboratory tests (CBC, liver/renal function tests, IS trough levels) for other respective secondary endpoints (hematologic, liver/renal function) every 1-2 weeks. Clinical laboratory tests for other endpoints (hyperlipidemia- lipid profiles, diabetes- HbA1C, proteinuria- urine protein/creatinine) will be performed pre-EVL addition and at 6 months ( $\pm$  1 month) post-LT, all per our standard of care. Routine clinic visits will occur per standard of care (1, 2, 3, 4 & 6 months) to monitor for side effects and document any adverse events, in addition to our research coordinators maintaining close communication with the patients. The study will be completed at 6 months ( $\pm$  1 month) post-LT, which will include final assessments of clinical and laboratory outcomes. Case report forms and electronic databases documenting all immune assay results and clinical data/outcomes will be utilized for all endpoint comparisons.

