#### **7.4.4 Laboratory evaluations**

At liver transplant donor/recipient collection of lymph nodes and liver biopsy tissue will take place if the patient is consented prior to transplantation. Liver biopsy tissue will also be collected at the time of a suspected rejection.

Blood samples for flow cytometry, PBMCs, RNA and sera will be collected at visits 3, 4, 5, 6, 7 and rejection.

Standard SOC laboratory tests will be performed per our transplant center post-LT protocol: CBC, CMP, trough IS levels three times weekly (0-1 month post-LT), two times weekly (1-3 months post-LT), one time weekly (3-6 months post-LT).

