i) Blood Immunophenotyping. The approach will be to conduct flow cytometry immunophenotyping of peripheral blood before TAC-WD initiation (1 to 2 months and 3 months ( $\pm$  1 month)), right at total TAC-WD (4 months ( $\pm$  1 month)), 2 weeks after full TAC-WD (4.5 months ( $\pm$  1 month)) and study end (6 months ( $\pm$  1 month)) post-LT to analyze cellular changes. Methods: The Immune Monitoring Laboratory at NU (Co-Director [name]) will perform the immunophenotyping. PBMC are isolated from heparinized 30 cc samples on Ficoll-Hypaque gradients. Surface markers are detected with monoclonal antibodies for the T cell subsets CD3, CD4, CD8, CD25, CD45RA, CTLA4 and CD127 followed by fixation/permeabilization/incubation with human FOXP3 antibodies and final flow cytometric analysis. RBC-lysed peripheral blood is also labeled with monoclonal antibodies for T cell subsets, naïve/memory/regulatory B cells (CD19, CD27, IgD, IgM, IL-6), monocytes (CD14) and NK cells (CD56) to quantify the absolute cell numbers per  $\mu$ L. In addition, dendritic cell surface markers are analyzed as follows: monocyteoid vs. plasmacytoid (CD11c; CD123) ratio; antigen processing markers (CD83; CD205); markers inducing Tregs (ILT3; ILT4). For statistical analysis, we perform within subject comparisons on PBMC for both successful and failed TAC-WD/EVL groups using appropriate paired analysis (paired t-test or Wilcoxon Signed Rank test). For the main hypothesis testing, repeated measures of analysis of variance (RM-ANOVA) are used to test the trajectory variations between the groups on PBMC over time. Two-sided F-test statistics are applied;  $\alpha=0.05$  (stats by NU Transplant Statistician).

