### 10.3.3 Biomarkers/Studies Planned

*i) Blood Immunophenotyping.* The approach will be to conduct flow cytometry immunophenotyping of peripheral blood before TAC-WD initiation (3 months ( $\pm$  1 month)), right at total TAC-WD (4 months ( $\pm$  1 month)), 2 weeks after full TAC-WD (4.5 months ( $\pm$  1 month)) and study end (6 months ( $\pm$  1 month)) post-LT to analyze cellular changes. Methods : The Immune Monitoring Laboratory at NU (Co-Director [name]) will perform the immunophenotyping. PBMC are isolated from heparinized 30 cc samples on Ficoll-Hypaque gradients. Surface markers are detected with monoclonal antibodies for the T cell subsets CD3, CD4, CD8, CD25, CD45RA, CTLA4 and CD127 followed by fixation/permeabilization/incubation with human FOXP3 antibodies and final flow cytometric analysis. RBC-lysed peripheral blood is also labeled with monoclonal antibodies for T cell subsets, naïve/memory/regulatory B cells (CD19, CD27, IgD, IgM, IL-6), monocytes (CD14) and NK cells (CD56) to quantify the absolute cell numbers per  $\mu$ L. In addition, dendritic cell surface markers are analyzed as follows: monocyteoid vs. plasmacytoid (CD11c; CD123) ratio; antigen processing markers (CD83; CD205); markers inducing Tregs (ILT3; ILT4). For statistical analysis, we perform within subject comparisons on PBMC for both successful and failed TAC-WD/EVL groups using appropriate paired analysis (paired t-test or Wilcoxon Signed Rank test). For the main hypothesis testing, repeated measures of analysis of variance (RM-ANOVA) are used to test the trajectory variations between the groups on PBMC over time. Two-sided F-test statistics are applied;  $\alpha=0.05$  (stats by NU Transplant Statistician).

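### The primary biomarker analysis has two visit sets, and the one in Section 10.2 includes a month 1-2 sample that Table 7-1 makes optional

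*Combined protocol and SAP*

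**What the plan says.** Three places include the month 1-2 sample:

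- Section 10.2, immunophenotyping: "before TAC-WD initiation (1 to 2 months and 3 months", followed by months 4, 4.5 and 6. That makes five time points.
- Section 4: "Peripheral blood bioassays will be performed pre-TAC-WD (1 to 2 months and 3 months", followed by the later visits.
- Section 7.4.4: "Blood samples for flow cytometry, PBMCs, RNA and sera will be collected at visits 3, 4, 5, 6, 7 and rejection". Nothing here says that the Visit 3 sample is optional.

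Two places leave it out. Section 10.3.3 has "flow cytometry immunophenotyping of peripheral blood before TAC-WD initiation (3 months", then months 4, 4.5 and 6, which makes four time points. The synopsis gives the same four.

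Table 7-1 puts an asterisk on the Visit 3 blood, explained as "unfunded and not mandatory for this protocol". Its visit note says "Collect blood if possible (unfunded for this study". The blood samples at Visits 4 to 7 carry no such mark.

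The main test in 10.2 is stated as: "repeated measures of analysis of variance (RM-ANOVA) are used to test the trajectory variations between the groups on PBMC over time". The microarrays follow the immunophenotyping schedule in all three descriptions, so they inherit whichever visit set applies. Section 10.2.3 deals only with patients lost to follow-up. It has no rule for a single missed sample, and no mixed model or imputation is named anywhere.

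**The concern.** Two things are at stake.

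First, the two visit sets answer different questions. Everolimus is added, and mycophenolate stopped, at Visit 3. A five-visit trajectory therefore mixes the change after everolimus is added with the change as tacrolimus is withdrawn. A four-visit trajectory starts on the combination and isolates the withdrawal phase. With both in the plan, the analyst could choose between them after seeing the data, in the main hypothesis test.

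Second, classical repeated-measures ANOVA needs a value at every visit for each patient. Run on the five visits in 10.2, it removes anyone whose optional Visit 3 blood was not taken or not assayed. The group that limits this study is the failures, expected to number 4-5, so each lost patient matters.

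**Working it through.** **Inputs.** Section 10.4: 25 enrolled, 20 expected to enter tacrolimus withdrawal, of whom 14-15 are expected without rejection and 4-5 with it. Figure 6: 15 and 5. Section 3: rejection rate 20%, expected 1-2 months after withdrawal. The share of patients with a Visit 3 sample, *q*, is not in the documents and is assumed over a range.

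**The plan's own counts.** At 20%, 20 × 0.20 = 4 failures and 20 × 0.80 = 16 successes. These are close to the stated 4-5 and 14-15. Only 15 + 5 adds to 20, which is a 25% rate (5/20). I use 15 and 5, as in Figure 6; the point does not depend on this choice.

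**Complete cases on five visits.** Expected numbers are 20*q* overall, 5*q* failures and 15*q* successes. The chance that fewer than two of five failures remain is (1 − *q*)^5 + 5*q*(1 − *q*)^4.

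| Visit 3 missing (assumed) | *q* | Patients kept | Failures | Successes | Chance of fewer than 2 failures |
|---|---|---|---|---|---|
| 10% | 0.90 | 18 | 4.5 | 13.5 | below 0.1% |
| 25% | 0.75 | 15 | 3.75 | 11.25 | 1.6% |
| 50% | 0.50 | 10 | 2.5 | 7.5 | 18.8% |

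With four failures instead of five, the last column becomes 0.4%, 5.1% and 31.2%. These figures count Visit 3 losses only.

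**Without the Visit 3 requirement.** On Visits 4-7, a missing Visit 3 sample removes nobody, so all 20 stay. A mixed model on all available samples also keeps all 20. In one simulated data set of 20 patients and five visits, with 10 Visit 3 values removed, complete-case analysis kept 10 patients (2 failures, 8 successes). A random-intercept mixed model used 20 patients and 20 × 5 − 10 = 90 observations.

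**Is the four-visit set enough by itself?** Table 7-1 and Section 7.3 end participation at rejection. Counting 1-2 months from Visit 5 (day 120) puts the expected rejections at about day 150 to 180, after Visit 6 (day 135) but before or at Visit 7 (day 180). A failure who rejects before Visit 7 has no scheduled month 6 sample. If all five do, complete-case ANOVA on Visits 4-7 keeps 0 of 5 failures and 15 of 15 successes, and there is no comparison left. Changing the visit set without changing the method does not protect the failure group.

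**The case against.** The strongest reply is that the plan nowhere says patients without Visit 3 blood are deleted. The sentence naming the ANOVA lists no visits, and month 1-2 appears in the sentence on sampling. Section 4 reads as a collection list: it also includes samples at rejection, which cannot be a common visit in such a model. All of this stands. Deletion is a property of classical repeated-measures ANOVA on five visits, not a written rule, and a reader who infers that the plan prescribes it goes beyond the text.

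Nor does optional mean missing. Visit 3 is a standard-of-care visit, routine blood is drawn several times a week around then, and research blood is taken with routine draws, so collection could be nearly complete. If instead lack of funding means that Visit 3 is never assayed, that visit is absent for everyone and nobody is dropped. A reader might infer a particular heavy loss, such as a third or a half of samples, but no document supports one figure over another.

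It is also arguable that Table 7-1 does not control: the Figure 6 footnote lists unfunded samples only at transplant and at rejection. Visit 3 is also the only scheduled post-transplant sample around the start of everolimus, in a study whose premise is that everolimus promotes immunoregulation. These are reasons to keep the sample as exploratory. They do not remove the conflict between sections.

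Finally, this is an unpowered pilot meant to find time points for a larger trial. That lowers the stakes and explains the absence of a power calculation. It does not explain two definitions of the main test.

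**Conclusion.** The inconsistency holds on the current text. Section 10.2, with Section 4 and 7.4.4 on sampling, includes month 1-2; the synopsis and 10.3.3 do not; Table 7-1 makes the sample optional. The microarrays share the conflict.

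The loss of patients is conditional. It occurs if classical repeated-measures ANOVA is run on all five visits and some Visit 3 samples are absent. Its size cannot be taken from the documents; the table above is a range under assumed missingness, not a forecast.

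A reader might also infer that confining the ANOVA to Visits 4-7 settles the matter. It does not, because participation ends at rejection and failures who reject before Visit 7 would still be removed from a complete-case analysis. Both the visit set and the method need stating. This should be corrected before the data are analysed, but it does not undermine the study.

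**What to change.** - Name one visit set for the primary analysis: Visits 4-7, as in the synopsis and 10.3.3, or Visits 4-5 where the aim is prediction. State that the microarrays use the same set.
- Remove month 1-2 from the primary time points in 10.2, and align Section 4 and 7.4.4 with Table 7-1. Describe any Visit 3 sample as an exploratory pre-everolimus value.
- Replace complete-case repeated-measures ANOVA with a mixed model (group, visit, their interaction, and a patient effect) fitted to all available samples. Extend 10.2.3 to cover a single missed sample and samples not taken because participation ended at rejection.
- State the limit of this: the model keeps patients with incomplete series, but it cannot supply a month 6 mean for failures if no failure is sampled then. The Visits 4-5 comparison is least exposed to this.

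The cost is wording in four sections, a little more analysis work, and a less prominent role for the pre-everolimus sample. No extra samples or funding are needed.

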## **7.1 Patient demographics/other baseline characteristics**

Basic demographics (age, sex, race, cause of liver disease, past medical history) and laboratory values will be determined prior to enrollment. To determine continuation criteria at one to two months and three months ( $\pm$  1 month), the medical charts will be reviewed to determine laboratory values and ensure inclusion/exclusion criteria are met. Throughout the trial, history and physicals per standard of care will be performed at most of the study time points (see schedule above) as well as laboratory values.

